2.2.3 MicroRNA profiling and metabolic disease

MicroRNAs (miRNAs) are small 22–25-nt-long noncoding RNA molecules that negatively regulate translation of target messenger RNAs. miRNAs normally bind to their target messenger RNA (mRNA) leading to translation inhibition and/or mRNA degradation (34). Over 500 miRNAs have been found in the human genome (35), and it has been estimated that they could regulate 74–92% of all protein coding mRNAs (36). By affecting gene regulation, miRNAs are likely to be involved in most biological processes, and aberrant expression of miRNAs has been implicated in numerous disease states including insulin resistance and type 2 diabetes. Several studies have identified

dysregulation of several miRNAs in animal and human type 2 diabetes, in insulin sensitive tissues such as adipose tissue (37). The discovery of circulating miRNAs has highlighted their potential as both endocrine signalling molecules and disease markers (38). MicroRNA expression has been implicated in the complex interplay between genetic susceptibility to disease and environmental factors. We aim to undertake the novel exploration into the impact of early nutrition on microRNA expression and correlate this with body composition, by global microRNA profiling at the time of discharge.

2.2.4 Human milk versus preterm formula: neurodevelopmental consequences

Accumulating evidence shows that poor early postnatal growth is associated with impaired neurodevelopment in preterm infants (39-42). Suboptimal nutritional intake and subsequent poor growth including brain growth has lasting consequences in this sensitive period. Follow-up studies showed that at 7 years of age, preterm infants randomised to receive standard formula from birth to discharge, demonstrated neurocognitive impairment with a significant reduction in IQ compared with infants randomised to receive enriched formula (39). Despite slower growth in breast milk fed preterm infants, there is a growing body of evidence which suggests that neurocognitive outcome is better. Long-term studies at 8 years of age through adolescence suggest that intelligence test results and white matter and total brain volumes are greater in subjects who had received human milk as infants in the neonatal unit.(39,43). Extremely preterm infants receiving the greatest proportion of human milk in the neonatal unit had significantly greater scores for mental, motor, and behaviour scores at ages 18 months and 30 months. (44,45) These data remain significant after adjustment for confounding factors, such as maternal age, education, marital status, race, and infant morbidities.

Evidence for neurodevelopmental advantage in the use of HDM used as sole diet or to supplement MOM, compared to PTF however, is less clear. In a meta-analysis of donor breast milk versus preterm formula for preterm infants, only one trial compared neurodevelopment as the outcome, and there were no significant differences in neurodevelopmental status at 9 or 18 months either used as sole diet or to supplement MOM (3). Indeed, the use of HDM, even with fortification, is consistently associated with slower growth compared to PTF (3, 4). The question of whether HDM has similar cognitive advantages as MOM, despite pasteurisation, and slower associated growth velocity compared to PTF, is worthy of further investigation.

2.2.5 Use of bovine fortifier for human milk

A Cochrane review (46) has shown that bovine multicomponent fortification of human milk in comparison to the unfortified human milk, improved short-term growth, but had no long-term advantage in terms of either growth or neurodevelopment, nor any clear effect on bone mineral content, and was not associated with clinically significant adverse effects. Fortification of human milk for preterm infants is now widely practiced, yet there exists widespread variation in its indication, method of initiation and indication for stopping (5). This reflects the lack of good evidence for optimal use.

Comparisons between fortified HM and PTF indicate that despite fortification, human milk fed preterm infants continue to grow slower than PTF fed infants (47, 48). Accumulating evidence suggests that a continuing protein deficit is primarily responsible for slow preterm growth (47,49) and there is growing concern that preterm protein requirements to maintain intrauterine growth rates and overcome catabolic deficits, is not being met (50). Recent ESPGHAN (2010) (51) guidelines have reflected this, recommending up to 4.5g/kg/d of protein for ELBW infants. Although a sole diet of preterm formula could match this intake, the assessment of protein intake from human milk is inherently difficult. The protein concentration of human milk decreases with gestational age and

duration of lactation but also varies unpredictably from sample to sample (52, 53). Furthermore, HDM is likely to have an even lower protein concentration than that from MOM as it is more likely to come from mothers of term infants. However, there is limited data on the macronutrient content of HDM, and we propose to analyse the macronutrient content of all HDM that each infant in the study receives, thus providing an accurate as possible nutritional intake for each interventional arm.

2.3 Bridging the gap

To begin to address these questions this feasibility pilot trial will assess growth and key candidate markers of long term metabolic health such as body composition, blood pressure, hepatic lipid content, QUICKI, metabolomic profile, in preterm infants randomised to receive PTF, fortified or unfortified HDM when there is a shortfall of MOM. An estimation of macronutrient content of HDM will be made by analysis of all HDM given to each infant in the HDM arm. To our best knowledge through wide professional and academic contacts, and searches of international registers, no trials similar to that which we propose are being undertaken in the UK or elsewhere.

2.4 Importance to the NHS

Infant nutrition studies involving randomisation, testing causality and unravelling biological mechanisms are rare. Yet infant nutrition is a cardinal candidate effector of long-term health. Current practice in feeding the preterm infant invariably involves the use of fortified Human Donor Milk or Preterm Formula. There are however no national standards or guidelines for enteral feeding of extremely preterm infants, and clinical practice is very variable.

Advocates of pasteurised HDM believe this is as efficacious as MOM in reducing two of the most feared conditions in newborn medicine, necrotising enterocolitis and bloodstream infection, and in improving long-term metabolic health. These result in major health services utilisation costs and a life-long burden of impairments on survivors.

An adequately powered trial is required to address these outcomes but poses two major hurdles, recruitment of large numbers of babies, and long-term follow-up. The organisation of NHS neonatal specialist care and the establishment of the Neonatal Data Analysis Unit that holds and archives national neonatal data at Chelsea & Westminster Hospital, and has received permission for the National Information Governance Board to link this to Hospital Episode statistics data, offers unique international opportunity to conduct this trial in the UK and achieve long term follow-up at low cost. Clarification of efficacy will advance clinical care, and enable economic evaluation and rational development of Human Milk Banking.

3. Aims and Hypothesis

Specific aims of this pilot trial are to:

A: Assess feasibility

- 1) test the acceptability of the trial design with parents and clinicians
- 2) test that recruitment to target is achievable, estimate consent and dropout rates
- 3) estimate the trial requirement for HDM from NHS Human Milk Banks
- 4) test that clinical outcome data can be retrieved from operational NHS electronic records, thus minimising the burden of data capture and facilitating the use of linked NHS records to achieve long-term follow-up at low cost.

B: Obtain data on the magnitude of effect at term equivalent age and again at term plus 6 weeks of age, on key mechanistic outcomes:

- 1) the primary outcome of total body adiposity, addressing the null hypothesis: there are no differences in total body adiposity, as measured by whole body MRI, between infants randomised to receive fortified MOM+/-HDM, unfortified MOM+/-HDM, or MOM+/-PTF.
- 2) the secondary outcomes of
 - Regional adiposity, as measured by whole body MRI
 - Non adipose tissue, as measured by whole body MRI
 - Total brain volume, as measured by MRI
 - Anthropometry (weight, length, and head circumference)
 - IHCL, as measured by magnetic resonance spectroscopy
 - blood pressure
 - Stool and urine metabolomic profile
 - Blood Quantitative Insulin Sensitivity Check Index (QUICKI) – at discharge only between infants randomised to receive fortified MOM+/-HDM, unfortified MOM+/- HDM or MOM+/-PTF.

C: By using HDM with known macronutrient content, we aim to correlate macronutrient intake of each intervention with the above outcomes.

4. Methods

4.1 Design

This will be a pilot single centre randomised controlled trial. There will be no novel interventions, merely randomisation of infants to three existing, widely used, standard feeding practices. For the purposes of clarity, this study will be in two parts. The first part will involve an opt out of feeding randomisation. Eligible preterm infants will be randomised by 48 hours to receive unfortified Mother's Own Milk (MOM) +/- Human Donor Milk (HDM), fortified MOM +/- HDM, or MOM +/- Preterm Formula (PTF), where HDM or PTF are used to make up any shortfall in MOM. Anthropometric and blood pressure outcomes will be determined from routinely collected clinical data. The second part will involve informed consent for collection and analysis of urine, stool, and blood samples and magnetic resonance imaging scans. The flowchart illustrates exactly what is involved if an infant is in the study.

4.2 Study Flowchart

Please see page 12

4.3 Patient Population:

Preterm infants born between 25+0 and 31+6 weeks gestational age.

4.3.1 Inclusion Criteria

- Preterm infants whose mothers are resident within the north west neonatal network, born between 25+0 to 31+6 weeks gestational age

4.3.2 Exclusion Criteria

- Major congenital or life threatening abnormalities or congenital abnormalities that preclude early milk feeding
- Inability to randomise infant within 48 hours
- Infants less than 25+0 weeks or more than 31+6 weeks

4.4 Screening and enrolment

For part one of the study, we plan to randomise all eligible infants, unless explicitly requested by the parents for their baby not to take part. Where possible parents will be approached before delivery, and the study explained to them eg for mothers at risk of premature delivery. In all cases, the study will be explained to the parents by one of the clinical team or study investigators shortly after birth, and a written parent information leaflet (PIL pt 1) will be given to the parents. This process will be documented in the infant's medical notes by the person explaining the study, with a confirmation sticker. Randomisation to one of the three feeding arms will take place between 24-48hrs of age.

[figure not shown]
For part two of the study, parents will be approached by one of the clinical team or the study investigators after 48hrs of age, and part two of the study will be explained to them, with a written parent information leaflet (PIL pt 2) given to them. At a convenient time for the parents, informed consent will then be sought for part 2 of the study. All infants will be recruited from the Chelsea and Westminster Hospital Neonatal Unit.

4.5 Explanation and informed consent for the study

Explanation and informed consent requires individual discussion with the infant's parents about the nature of the research to be conducted in a language that is easy to comprehend. The parents will have the study verbally explained to them and also be given a written information sheet about the study. The parents will have sufficient time to think about the study and ask any further questions regarding it. It will be stressed to parents that their babies will follow one of three, widely used, standard feeding practices, and there will be no new treatments or interventions. The parents will also understand that refusal to participate in the study will not affect the quality of subsequent medical care and if they do consent to participate they may withdraw at any point without affecting their infant's care.

Before any trial-related procedures may be performed, informed consent must be obtained from the infant's parents by the investigator by means of a signed declaration. The investigator must record in the case report form to confirm that informed consent was obtained and store the original of the signed declaration of consent in the patient's notes. A copy will be given to the infant's parents and a copy filed in the investigator file.

4.1 PREMFOOD Flowchart

4.5 Explanation and informed consent for the study

Explanation and informed consent requires individual discussion with the infant's parents about the nature of the research to be conducted in a language that is easy to comprehend. The parents will have the study verbally explained to them and also be given a written information sheet about the study. The parents will have sufficient time to think about the study and ask any further questions regarding it. It will be stressed to parents that their babies will follow one of three, widely used, standard feeding practices, and there will be no new treatments or interventions. The parents will also understand that refusal to participate in the study will not affect the quality of subsequent medical care and if they do consent to participate they may withdraw at any point without affecting their infant's care.

Before any trial-related procedures may be performed, informed consent must be obtained from the infant's parents by the investigator by means of a signed declaration. The investigator must record in the case report form to confirm that informed consent was obtained and store the original of the signed declaration of consent in the patient's notes. A copy will be given to the infant's parents and a copy filed in the investigator file.

4.6 Randomisation

Randomisation will be generated centrally using a computer program, with minimisation by infant sex, gestational age (25-27+6 wks, 28-31+6 wks) birth-weight Z score (<-1.28, >-1.28) Randomisation will take place between 24-48hrs of age. Infants will be randomised to receive either HDM or PTF to make up any shortfall in Mother's Own Milk (MOM) until 34+6 weeks postmenstrual age. Blinding of the intervention is not practicable because of the distinctive appearances of human milk and formula, and the method of administration to preterm babies by syringe and nasogastric tube. At 35 weeks, the infant will be close to discharge, and feeding will be directly from the breast or formula by bottle in accordance with maternal choice.

4.7 Withdrawals and protocol violations

4.7.1 Temporary discontinuation of feeds/alternative feeds

Infants in the trial may develop feed intolerance or suspected/confirmed necrotising enterocolitis (NEC) requiring the cessation of enteral feeds. The period of no feeding may vary from a few hours to a number of days. Once feeding is re-established, the infant will continue with the allocated interventional arm. However, there may be circumstances in which continuation of the allocated feed is deemed inappropriate by the clinical team. Examples would include feed intolerance and the use of hydrolysed or elemental feeds. Infants would remain in the study and included in the "intention-to-treat analysis."

4.7.2 Withdrawal of infant from trial procedures and incomplete follow-up

It is possible that parents may choose to withdraw their infant from trial procedures resulting in incomplete patient follow up and failure to capture outcome data. Likewise, if an infant dies before discharge or is still on the neonatal unit and considered too unstable at term equivalent age or term plus 6 weeks, they will not have their MRI scan.

4.8 Trial intervention

4.8.1 Description

The interventions will be fortified, or unfortified pasteurised Human Donor Milk (HDM) with the comparator Preterm Formula (PTF) to make up any shortfall in Mother's Own Milk (MOM).

4.8.2 Feeding schedule

The trial is designed to reflect current clinical practice. Preterm infants will be introduced to parenteral nutrition and enteral feeds within the first 24 hours of birth. Milk volumes will be increased up to 200ml/kg/day in accordance with a standard protocol modified if necessary in accordance with infant tolerance; parenteral intake simultaneously decreased. For infants randomised to fortified MOM± HDM, fortification will begin when a total enteral intake of 100ml/kg/day is reached and continued to 34+6 weeks postmenstrual age. At this point feeding will progress in accordance with maternal choice.

4.8.3 Pasteurised Human Donor Milk

The Chelsea and Westminster Hospital neonatal unit obtains all HDM from the Countess of Chester Human Milk Bank. The milk bank follows the recommendations for donor screening, pasteurisation, milk collection and storage published by NICE 2010 (54). All HDM supplied has been analysed for macronutrient content using infrared spectrometry done at the Countess of Chester Human Milk Bank. All bottles will be labelled with their macronutrient content and daily intakes recorded on the clinical case report form. If an infant is allocated to the HDM intervention, then the instruction only to use HDM to supplement MOM will be made on the infants feeding plan.

4.8.4 Fortified Human Milk

For infants randomised to receive fortified HDM to supplement MOM, all milk will be fortified once a total enteral intake of 150ml/kg/d is reached. This will be with a multicomponent bovine breast milk fortifier (Cow and Gate Nutriprem Breast Milk Fortifier). The amount used will be in accordance with current practice, namely two sachets per 100ml.

4.8.5 Unfortified Human Milk

For infants randomised to receive unfortified human milk the instruction to only use unfortified HDM to supplement unfortified MOM will be made on the infants feeding plan. For these infants, the situation may arise where the growth of the infants is deemed suboptimal by the clinical team. Therefore, weight gain will be assessed two weeks after a milk volume of 120ml/kg/d has been reached. At this point, if the infant has crossed down 3 centile bandwidths from birthweight centile bandwidth, or shows continued downward crossing if less than the 0.4th centile, using birthweight centile charts, then the

infant will discontinue the feeding intervention. There may be other causes of poor weight gain than inadequate enteral nutrition. These include for example, respiratory distress syndrome, infection, chronic lung disease, gastro-oesophageal reflux disease, anaemia, patent ductus arteriosus, or underlying congenital anomaly. Once these causes have been excluded or corrected, and the weight loss has been confirmed from at least two weights over a 72 hour period, fortification will be commenced. Infants will then receive fortified HDM, and undergo all outcome measures. Analysis will be as per protocol, and also for categories of overall intake (see statistical analysis).

This three centile drop cut off value is based on results of a longitudinal preterm growth reference by Cole et al (submitted). This is a study of routinely collected growth data (co-ordinated by the Neonatal Data Analysis Unit) from 113 neonatal units across the UK from 2006-2011. A growth reference for weight, length, and head circumference in preterm infants less than 32 weeks from birth to term/near term was constructed, stratified for birth gestation week, and compared to currently used birthweight centile charts. In this comparison, average growth curves for all infants by week of birth gestation, crossed down 2-3 birthweight centile bandwidths over a period of 3-4 weeks from birth, before becoming parallel to the birthweight centile bandwidth curves. Time taken to reach full milk feeds will vary depending on feeding tolerance, but typically will take from a few days to a couple of weeks. A period of two weeks after full milk feeding (120ml/kg/d and above) has been reached, is therefore expected to coincide with no further crossing down in birthweight centile bandwidth curves.

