5.1 Regulatory framework

5.2 Research ethics approval and monitoring

5.3 Adverse events

5.4 Indemnity

5.5 Sponsor

5.6 Funding

5.7 Audit

5.8 Study Management

5.9 Publication policy

5.4 End of trial

6. References

1. Protocol summary

| | |
|----------------------------------|---|
| Title | A pilot randomised controlled trial of fortified Human Donor Milk (HDM), unfortified HDM, or Preterm Formula (PTF) in preterm babies, to make up any shortfall in the volume of Mother's Own Milk (MOM) |
| Study Centre | Chelsea and Westminster Hospital Neonatal Unit |
| Study Objectives | 
 1. To assess the feasibility of a multicentre trial addressing short term (Necrotising Enterocolitis and Bloodstream Infection) and long term (growth and metabolic) outcomes 2. To address the null hypothesis: there are no differences in total body adiposity, as measured by whole body MRI, between any groups of infants randomised to receive unfortified MOM+/-HDM, fortified MOM+/-HDM or MOM+/-PTF 3. To assess the macronutrient content of HDM given to each infant in the HDM arms by analysis of HDM samples |
| Study Design | Single centre unblinded randomised controlled trial |
| Study Population | 
Inclusion Criteria
 
 • Preterm infants born between 25+0 to 31+6 weeks gestational age 
Exclusion Criteria
 
 • Major congenital or life threatening abnormalities or congenital abnormalities that preclude early milk feeding • Inability to randomise infant within 48 hours |
| Intervention | 
Either
 
 1. HDM, fortified with standard commercial multicomponent breast milk fortifier, once enteral intake of 150ml/kg/d reached, to supplement MOM 
Or
 
 2. Unfortified HDM to supplement MOM |
| Comparator | PTF to supplement MOM |
| Target number of patients | 84 (28 in each group) |
| Randomisation | 
 • Using minimisation • Stratifying factors are: gestational age (25-27+6 w and 28-31+6 w), birth weight z score (<-1.28, >-1.28) and sex |
| Primary outcomes | 
 • Total body adiposity, as measured by whole body MRI, at term equivalent age |

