4.11.2 Statistical analysis

Outcomes will be analysed both for by intention to treat and as per protocol using multiple linear regression with adjustment for covariates where appropriate. Baseline covariates such as gender, gestational age, and birthweight z score, will be controlled for by randomisation stratification, while those such as ethnicity will be adjusted for. To address the null hypothesis differences between groups will be tested using ANOVA, with examination of the 3 pairwise differences for magnitude of differences. For the purposes of modelling randomised babies will be assigned to categories of overall intake (predominantly MOM, predominantly PTF, predominantly HDM). Results will be presented as estimates and 95% confidence intervals for differences in means.

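### Does the plan lose the as-randomised comparison for unfortified-arm infants who start fortifier because of poor weight gain?

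*Combined protocol and SAP*

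**What the plan says.** Section 4.8.5 sets a weight check for the unfortified arm. The trigger applies "if the infant has crossed down 3 centile bandwidths from birthweight centile bandwidth", or on continued downward crossing below the 0.4th centile. Other causes must then be excluded or corrected and the weights confirmed over 72 hours. After that, "Infants will then receive fortified HDM, and undergo all outcome measures". The analysis sentence for these infants is "Analysis will be as per protocol, and also for categories of overall intake (see statistical analysis", and its closing bracket sends the reader to 4.11.2.

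Section 4.11.2 states: "Outcomes will be analysed both for by intention to treat and as per protocol using multiple linear regression". It calls neither analysis primary, does not define the per-protocol set, and does not say which set the ANOVA uses. For modelling, "randomised babies will be assigned to categories of overall intake (predominantly MOM, predominantly PTF, predominantly HDM"; fortified and unfortified donor milk share one category.

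Section 4.7.1 deals with infants for whom the clinical team judges the allocated feed inappropriate: "Infants would remain in the study and included in the" intention-to-treat analysis. The examples it gives are feed intolerance and hydrolysed or elemental feeds.

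The Protocol summary states the null hypothesis as no difference in total body adiposity "between any groups of infants randomised to receive unfortified MOM+/-HDM, fortified MOM+/-HDM or MOM+/-PTF". Section 3 frames it the same way.

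**The concern.** The switch happens in one arm only and depends on weight gain after randomisation, which may be related to adiposity. The one analysis sentence written for these infants names a per-protocol and an intake-category analysis and omits intention to treat. With the per-protocol set undefined, an analyst could keep the switchers (the protocol itself orders the switch) or drop them. Dropping them selects on a post-randomisation variable in an unblinded trial, and the choice could be made after the data are seen.

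Switching might not be rare. The growth reference quoted in 4.8.5 reports that average curves "crossed down 2-3 birthweight centile bandwidths over a period of 3-4 weeks from birth", close to the 3-bandwidth trigger. At stake is the fortified-versus-unfortified difference in adiposity. Section 4.11.1 makes the magnitude of effect on adiposity an aim, and section 2.1 says the pilot is to inform an application for a trial of about 4000 babies.

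**Working it through.** **1. Which analyses contain the switchers?**

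| Section | What it implies for switchers |
|---|---|
| 4.8.5 | Outcomes still measured; analysed as per protocol and by intake category; refers to 4.11.2 |
| 4.11.2 | Outcomes analysed by intention to treat and per protocol, with no exception for any infants |
| 4.7.1 | Infants taken off the allocated feed stay in the intention-to-treat analysis; the list of examples is open-ended |
| Protocol summary and section 3 | Hypothesis concerns groups as randomised |

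No passage removes switchers from the intention-to-treat analysis. Read together, the sections give an as-randomised estimate that includes them, plus a per-protocol estimate whose handling of them is unstated. The words used in 4.8.5 may even mean only that analysis follows the protocol.

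**2. The plan's own figure.** Inputs from 4.11.1: SD 0.243 l, difference 0.243 l, 22 scanned infants per group, Bonferroni for three pairs. Two-sided alpha = 0.05/3, critical value 2.394.

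- Standard error = 0.243 × √(2/22) = 0.073 l
- Power = Φ(0.243/0.0733 − 2.394) = Φ(0.92) = 82.2%, against 82.4% in Table 3 (82.4% exactly with alpha rounded to 0.017)

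The figure reproduces.

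**3. Effect of switching on the as-randomised contrast.** The switch rate x is assumed. In the limiting case a switcher takes the full fortified-arm mean, so the contrast is (1 − x) × 0.243 l.

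| Assumed x | Contrast (l) | Power |
|---|---|---|
| 0% | 0.243 | 82.2% |
| 5% | 0.231 | 77.5% |
| 20% | 0.194 | 60.2% |
| 30% | 0.170 | 47.1% |

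If a switcher takes only half the effect, 20% switching leaves (1 − 0.10) × 0.243 = 0.219 l and 72.3% power. This dilution comes from the feeding rule. It is the same whether or not the wording on analysis is tightened.

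**4. Effect of dropping switchers from a per-protocol set.** Assume no true effect, that switchers are the lowest tail of weight gain, and a correlation r between weight gain and adiposity. With φ the normal density at the x quantile, the shift in the unfortified mean is r × φ/(1 − x) × SD.

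- x = 5%, r = 0.3: 0.033 SD = 0.008 l
- x = 20%, r = 0.5: 0.5 × 0.280/0.80 = 0.175 SD = 0.043 l
- x = 30%, r = 0.7: 0.348 SD = 0.084 l

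The middle case is 0.043/0.073, about 0.6 of a standard error. A negative r reverses the sign. The exclusion and confirmation steps in 4.8.5 mean that real switchers are not simply the lowest tail, so real shifts are probably smaller.

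**5. Would dropping switchers protect power?** With 22 v 17.6 infants, the standard error is 0.243 × √(1/22 + 1/17.6) = 0.0777 l and power for 0.243 l is 76.8% before bias. Including the 0.043 l shift, the contrast is 0.200 l or 0.286 l, depending on the direction of the true effect. Power is then Φ(0.200/0.0777 − 2.394), about 57%, or Φ(0.286/0.0777 − 2.394), about 90%. The apparent advantage over 60.2% is not dependable, so an analyst has no good statistical reason to prefer the dropped set to the randomised comparison.

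**The case for a change.** The strongest contrary case is that planning two analyses, ranking neither and defining only one of them by convention leaves room to choose after seeing the data. The intake categories cannot close the gap, because they do not separate fortified from unfortified donor milk. If switchers were moved into the fortified group, the contrast under the same 20% and 0.5 assumptions would shift by 0.5 × 0.280 × (1/1.2 + 1/0.8) = 0.292 SD = 0.071 l, about one standard error. A few sentences would settle the matter and would need no new data.

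Part of this stands. Section 4.11.2 names no primary analysis and does not say what the per-protocol set is, and the intake categories cannot identify switchers. The rest carries less weight. Neither 4.8.5 nor 4.11.2 proposes moving infants between arms, so the 0.071 l scenario has no basis in the text. The average drop of 2-3 bandwidths describes curves by week of birth gestation in routine data. The same section expects downward crossing to have ended by the time of the check, so the reference does not give a switch rate. Having two estimates is the ordinary result of planning both analyses. The extra wording would label, define or report analyses already planned; it would alter no method, dataset or stated figure.

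**Conclusion.** The concern does not call for a change. The as-randomised comparison, with switchers included, is already planned: 4.11.2 covers all outcomes, 4.8.5 refers to it and keeps the outcome measurements, 4.7.1 supports it in general terms, and the hypothesis is stated by randomised group. An analyst would answer the hypothesis with that comparison and describe how switchers were handled in any per-protocol result.

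The remaining gap concerns only the undefined per-protocol set. Under assumed switching of 5-30% and correlations of 0.3-0.7, dropping switchers would shift the unfortified mean by 0.008-0.084 l in that analysis alone. These figures are illustrations; neither the size nor the direction of any bias can be derived from the documents. Sections 4.11.1 and 4.11.2 describe a feasibility pilot that is likely to be underpowered and that reports estimates with 95% confidence intervals. No documented go/no-go rule depends on the choice. Infants without a scan are a separate matter and do not bear on this conclusion.
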